created for this project, on the same schedule as peer mentoring sessions. Both conditions will be delivered via Webex, which has several advantages for this intervention: 1) Sessions are easily accessible via phone or computer, allowing participants to choose their preferred interaction style; 2) A study coordinator can host the support groups and drop in/out for monitoring purposes; 3) There are video- or voice-call options for up to 25 participants at a time; and 4) This application ensures concordant delivery methods across both arms of the study and the ability to document the frequency that voice and video options are used to adjust for participant choices in analyses. All participants (mentees, mentors, and social support controls) will be assessed using validated measures of patient reported outcomes and clinical indicators of disease activity at baseline, mid-intervention (3 months from baseline), immediately post-intervention (6 months from baseline), and 6 months post-intervention (12 months from baseline). For each wave, outcomes for mentees randomized to the mentored group will be compared with the outcomes of mentees randomized to the support group. A booster session will be incorporated for all participants (mentored and support group) at 3 months post-intervention to encourage retention.[102]

B4c. Scientific Rigor: Assuming 3 post-randomization measurement time points, level of significance p=0.05, two-tailed comparison, correlation between pairs of measurements within participants (interclass correlation) no larger than p=0.7, AR(1) covariance structure, we estimate that 123 participants per group (total n=246) are needed to detect, with 80% power, a standardized effect size of 0.35sd with 20% inflation for attrition at 12 months. This study will apply strict principles of randomized clinical trials including randomization, blinding, careful tracking of all participants and intent-to-treat analyses to ensure robust and unbiased results.

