**Data Collection Strategy** 

Data Collection Process/Schedule: Fourteen trained peer mentors will deliver the intervention in each wave and one full-time study coordinator (SC) will conduct screening, consent, enrollment procedures, and support group moderation. The primary method of data collection will be face to face interview. Mentees will be assessed at baseline, mid-intervention (3 months from baseline), immediately post-intervention (6 months from baseline), and 6 months post-intervention (12 months from baseline). Physical examination and laboratory evaluation will be achieved by in-person clinic visit when recent SLEDAI scores are not available in the database record of a given participant. Social support control participants will complete assessments on the same schedule as mentored participants. Given evidence that peer support may be just as beneficial to the supporters as it is to the person being supported, [118,119] mentors will be assessed on the same schedule as mentored and control participants, using the same tools.

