AIM 1: Determine the efficacy of a peer mentorship intervention in African American women with SLE on disease self-management and HRQOL. Analyses for Aim 1 will focus on estimation of efficacy as determined by: (a) change in quality of life; and (b) change in self-management. Estimates of effect sizes for outcome variables will be reported as point estimates (mean differences between pre-post measures. as appropriate) and interval estimates (95% CI) with two-sided p-vales denoting statistical significance to provide an indication of the presence of a clinically important treatment effect. [145,146] A p-value of 0.05 will be considered to be statistically significant. After studying the distributions of baseline characteristics. we will use a generalized linear mixed model regression model to determine if the intervention will produce a greater change in the main outcomes from baseline. This model will include time, treatment (along with their interaction), and covariates (including the amount of intervention received, demographic factors, medications, coping, depression, stress, anxiety, health literacy, trust, and social support) as fixed-effects. Using the amount of intervention, which is measured as an aggregate number of sessions completed or hours of interaction as a covariate would allow us to study the dose response. In the generalized linear mixed model (GLMM), we will use different link functions depending on the assumed distribution of the response variable. For binary outcomes, we will use logit link and for count outcomes we will use log link under a poisson or negative binomial distribution. For example, for the a given quality of life variable, HRQOL measured at baseline, month 3 and month 6, we will include intervention group, time, and time X intervention as the primary independent variables in the basic (unadjusted) model, and covariates that are not balanced at randomization (or a propensity score based on these covariates) will be added in the subsequent (adjusted) model to adjust for the possible confounding effect of these variables. Unadjusted and covariate-adjusted least squares means for each outcome variable will be compared at the primary time point (month 12) and at intermediate secondary time point (month 6) using appropriate model contrasts and the Tukey-Kramer adjustment for multiple comparisons for the secondary time points. These contrast comparisons, along with corresponding 95% CI, will provide estimates of the difference in outcome means (effect sizes) for the hypothesized comparisons.

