
AIM 2: Determine the impact of a peer mentorship intervention in African American women with SLE on clinical indicators of disease activity and clinical profile that indicates success of the intervention. Analyses for Aim 2 will focus on estimation of efficacy as determined by: change in disease activity of ≥4 point reduction from baseline in SLEDAI score, in concordance with the accepted SLE Responder Index (SRI).[147] For comparative statistical assessments, the two groups will be compared using a generalized linear mixed models (GLMM) approach.[148] This approach allows for measurement of participants at different time points, missing data under the assumption of missing at random (MAR), and can also account for the effect of correlated longitudinal measurements within participants. In addition, GLMM accommodates a wide range of distributional assumptions such as dichotomous (e.g. binomial), count (e.g. Poisson), continuous (e.g. Gaussian), and categorical or ordinal outcomes. Additionally, outcomes that are measured longitudinally (at 6 and 12 months) will have intervention group, time, and time-by-intervention group as primary independent variables in the model. Additional adjustment covariables will be added to the model in a second set of analyses, when indicated. The magnitude of between intervention differences in outcome variables (effect sizes) at each time point will be estimated using appropriate contrasts in the corresponding GLMM models. We will then perform a responder analysis to develop a profile of the clinical and laboratory characteristics that predict success of the intervention. For this, a multivariate regression logistic regression model where the outcome is success (/failure) and the difference in the clinical (SLEDAI components) levels over time are independent variables. We will use model selection approaches such as the all subsets selection, to identify the important clinical and laboratory features in the presence of others. As much as the data allows, we will also consider interactions of the SLEDAI components. As an alternative to logistic regression, we will also consider other approaches such as the CART, or logic forest to efficiently identify the clinical and laboratory characteristics that predict intervention success.

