Missing data: We will handle missing data using several techniques including multiple imputation and maximum likelihood,[149] and latent class based multiple imputation.[150] Missing data mechanisms will be examined using both univariate and multivariate methods. We will check for missing at random (MAR) by creating a missing indicator for each missing variable and study the predictors of missingness using logistic regression. If any of the fully observed covariates or outcomes become significant in the missing data model then we will use methods for MAR if we do not have any reason to believe that the missing data mechanism is not at random.

Mid-point Analyses for the protection of participants: In an effort to protect both mentors and mentees from potential deleterious effects of mentoring, a mid-point (interim) analysis will be undertaken to assess safety using 3-month post-intervention data. If mentored participants have worsened beyond a threshold, we will stop the trial for ethical concerns. For instance, if the lower confidence limits based on 95% confidence interval at the midpoint, for any one of the variables, namely depression, anxiety, and/or disease activity, is larger than 50% compared with their baseline measure, the trial will be terminated. Similarly, mentors will be monitored for depression, anxiety, and disease activity and if a worsening trajectory is observed at mid-point analyses, they will be removed from the study.

AIM 3: Determine the cost and cost-effectiveness of a peer mentorship intervention on disease self-management, disease activity, and HRQOL, in African American women with SLE.

The cost of the intervention will be compared to the outcomes of the intervention 12 months post baseline. In order to compare with previous lupus studies,[151,152] Quality adjusted life years (QALYS) will be calculated for intervention and control groups based on the SF36 outcome which will be measured 12 months post baseline. The calculation will be based on an established peer reviewed method.[153] Measuring QALYS gained relative to cost of the intervention is the preferred outcome method for the American College of Physicians (ACP).[154]

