In an effort to protect both mentors and mentees from potential deleterious effects of mentoring, a midpoint (interim) analysis will be undertaken to assess safety using 3-month post-intervention data. If mentored participants have worsened beyond a threshold, we will stop the trial for ethical concerns. For instance, if the lower confidence limits based on 95% confidence interval at the midpoint, for any one of the variables, namely depression, anxiety, and/or disease activity, is larger than 50% compared with their baseline measure, the trial will be terminated. Similarly, mentors will be monitored for depression, anxiety, and disease activity and if a worsening trajectory is observed at mid-point analyses, they will be removed from the study.

The PI will document all study activities and communications and generate formal quarterly, annual and final reports that will be disseminated to the study team and NINR program officer. At least quarterly meetings will be held with the entire study team, for regular review of research progress and for general project oversight and guidance.

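### The interim safety stopping rule names data from about month 9, where no assessment is scheduled; the month-3 mid-intervention visit was probably meant

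*Combined protocol and SAP*

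**What the plan says.** The rule appears three times in the combined protocol and SAP. In the Overview of Statistical Analysis Plan, under Mid-point Analyses for the protection of participants, "a mid-point (interim) analysis will be undertaken to assess safety using 3-month post-intervention data". The human-subjects section repeats this under the same heading, and the safety-monitoring text repeats it again: "a midpoint (interim) analysis will be undertaken to assess safety using 3-month post-intervention data". The example threshold that follows is checked at a stated moment: "if the lower confidence limits based on 95% confidence interval at the midpoint", for depression, anxiety or disease activity. Crossing it ends the trial. Mentors who show a worsening trajectory at the same analysis are removed.

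Section B4b (Study Overview) sets the assessments at "baseline, mid-intervention (3 months from baseline), immediately post-intervention (6 months from baseline), and 6 months post-intervention (12 months from baseline"). The Data Collection Strategy agrees: "Mentees will be assessed at baseline, mid-intervention (3 months from baseline), immediately post-intervention (6 months from baseline"), with a last assessment at month 12. The study summary in the human-subjects section gives the same four times, and the safety-monitoring text lists the same four data junctures.

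The only event placed three months after the intervention is a retention activity: "A booster session will be incorporated for all participants (mentored and support group) at 3 months post-intervention to encourage retention".

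The Data Collection Schedule item of the human-subjects section differs. After baseline it lists follow-up only at month 6 (questionnaire only) and month 12 (questionnaire and blood).

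**The concern.** A stopping rule needs data that will exist when the rule is applied. Under the protocol's own labels this one points to a time with no scheduled measurement of any of its three variables. Staff following the text would either find nothing to analyse or have to choose another visit themselves.

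Timing also decides what the rule can achieve. A review during the intervention can shorten exposure for the women whose scores prompted it. A review after their sessions have ended cannot. It could still protect later waves, and also mentors who return, since Recruitment of Mentors intends to keep mentors across several groups of mentees. This is the only group-level stopping rule that the documents describe, so its data source should be unambiguous.

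**Working it through.** No sample size, power or error-rate figure bears on this point. The check is a timeline comparison.

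**Inputs**
- Intervention length: 12 sessions over 24 weeks (B4b).
- Label for the end of intervention: month 6 (B4b, Data Collection Strategy).
- Scheduled assessments: months 0, 3, 6 and 12 (same sections, and the study summary in the human-subjects section).
- Alternative list: baseline, then months 6 and 12 (Data Collection Schedule, human-subjects section).
- Time named by the rule: 3 months post-intervention.

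**Step 1: where the named data fall**
- By the protocol's labels: 6 + 3 = month 9.
- By a strict week count: 24 × 7 / 30.44 = 5.5 months, and 5.5 + 3 = month 8.5.

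**Step 2: comparison with the schedule**
- Month 9 is not in {0, 3, 6, 12}. It lies 3 months from both month 6 and month 12.
- Month 8.5 is not in the set either. The nearest visit is month 6, 2.5 months away.
- Neither value is in the alternative list {0, 6, 12}.

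**Step 3: which time was probably meant**
- The rule calls itself a mid-point analysis and applies its limit at the midpoint.
- One visit is labelled mid-intervention, at month 3.
- The Aim 1 analysis text treats month 3 as measured: "HRQOL measured at baseline, month 3 and month 6".
- The Power and Sample Size Justification calls the final endpoint 12 months post intervention, although follow-up ends 12 months from baseline. The same loose use of the term would explain the phrase here.
- Against this, B4b uses the expression literally for the booster session, and the alternative list has no month 3.
- The Aim 2 text refers to "outcomes that are measured longitudinally (at 6 and 12 months"), but that describes an efficacy model and does not rule out a month-3 measurement.

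The two readings differ by 9 − 3 = 6 months.

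**Step 4: illustration of what the timing changes**

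Assume one session every 2 weeks, a first session 0, 2 or 4 weeks after baseline, and month 3 = week 13. The documents give neither the start week nor the time needed to collect and review the data.

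| First session | Left at week 13 | Left at week 17 (4-week review lag) | Left at week 39 (month 9) |
|---|---|---|---|
| Week 0 | 12 − 7 = 5 | 12 − 9 = 3 | 0 |
| Week 2 | 12 − 6 = 6 | 12 − 8 = 4 | 0 |
| Week 4 | 12 − 5 = 7 | 12 − 7 = 5 | 0 |

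The last session falls 22 weeks after the first, so none remain at week 39 for any start up to 39 − 22 = week 17. The rule uses a group confidence interval, so data must be pooled. If enrolment within a wave is staggered, early starters would have fewer sessions left than the table shows.

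**The case against.** The strongest reply is that this is a slip of terminology. The heading and the threshold sentence both say mid-point, one visit carries the mid-intervention label, and a sensible team would use month 3. This is probably the correct reading, but it does not remove the defect. The phrase is repeated in all three statements of the rule, the same expression is used literally for the booster, and the human-subjects follow-up list has no month-3 assessment to fall back on.

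Three stronger readings are tempting, and the documents do not support them.

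- *The rule would have no data at all.* Methods for Aim 2 says that SLEDAI scores are collected at regular visits and stored in the lupus database, so some disease-activity values could exist near month 9. What is missing is scheduled data. No PHQ-8 or GAD-8 is planned at that time.
- *Participants would be unprotected.* The human-subjects section provides depression and anxiety screening before pairing, clinician assessment after a positive depression screen, referral routes, bi-weekly contact by the principal investigator, and adverse-event collection throughout. These safeguards continue whichever month is meant. They act on individuals, however, and do not supply the group-level scores that the rule needs.
- *The repair requires SLEDAI and blood at every visit.* The rule's three variables can all be covered by questionnaire: PHQ-8 and GAD-8 (covariates section) and SLAQ (Methods for Aim 2). Recruitment of Mentees lets women outside the MUSC system take part without travelling there, so a blanket clinic-visit requirement would conflict with that.

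It is also fair to say that the threshold is introduced as an example, and that the session counts above rest on assumed start and review times.

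**Conclusion.** The concern holds as an inconsistency in a stated safety rule, and it should be corrected. Two facts are firm. Month 9 is none of the four scheduled assessments and falls after that wave's sessions. Month 3 is a scheduled visit during the intervention under the main schedule. That month 3 was intended is well supported but remains an inference for the sponsor to confirm.

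The illustrative counts (5 to 7 sessions left at month 3, 3 to 5 after a 4-week lag, none at month 9) show the direction of the effect and should not be read as estimates. The plan also does not say which of the three waves the analysis covers. That is an omission of lesser weight, and the named time is unscheduled whichever wave is meant. The 50% threshold is not questioned here.

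**What to change.** Subject to the sponsor's confirmation:

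1. In all three statements of the rule, replace the reference to data three months post-intervention with *data from the mid-intervention assessment, 3 months from baseline*.
2. In the Data Collection Schedule item of the human-subjects section, add a month-3 questionnaire containing the PHQ-8, GAD-8 and SLAQ, so that the rule has scheduled data for each of its variables.
3. As a minor clarification, state which wave or waves the interim analysis covers.

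Methods for Aim 2 plans SLEDAI at the mid-intervention point, while the human-subjects list has no month-3 visit and marks month 6 as questionnaire only. The sponsor should resolve that difference separately, bearing in mind the women who take part without travelling. The stopping rule does not depend on it.

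The cost is one phrase in three places, one entry in a list and one sentence on waves. Against B4b and the Data Collection Strategy, no visit is added. Against the human-subjects list as written, the addition is one questionnaire per participant at month 3.

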
study, the most valued aspect of the program was interaction with their peers, which informs the proposed intervention.

4. The Peer Approaches to Lupus Self-Management (PALS) Pilot Study. The PALS intervention was piloted with African American women with lupus enrolled in the SLE database at MUSC. Seven mentors were trained and paired with 21 mentees to provide modeling and reinforcement to participants by telephone for at least 60 minutes every week for 12 weeks. Mentee outcomes of self-management, disease progression (including disease activity, damage, and cytokine balance) were obtained at baseline, mid-intervention (6 weeks from baseline), and immediately postintervention (12 weeks from baseline), using validated tools. Qualitative data were also collected over the course of the study in the form of weekly mentee check-ins, mentor logs, and an end-of study focus group. While the PALS pilot lacked a control group, it provided a sense of general effect size and was used to design the current study.[107,108] At post-intervention, we observed statistically significant decreases in patient-reported disease activity (significant change score of 24,70 or 25% change in patient global assessment of overall lupus disease activity, p<0.001). incrementally improving trends in patient activation, and statistically significant decreases in depression (significant change score of 2.62 or 11% change in PHQ-8 score, p=0.05) and anxiety (significant change score of 3.52 or 15% change in GAD-8 score, p=0.018). Student t tests were also conducted to compare 2-month pre- and 2-month post-intervention hospitalization charges. Mean charges per person were \$24289 prior to intervention and \$872 post intervention, providing very strong evidence for the intervention's potential to reduce inpatient charges post intervention.[109] In addition, both mentees and mentors gave very high scores for perceived treatment credibility and service delivery, providing preliminary support for the efficacy, acceptability, and perceived credibility of the PALS intervention.[87,88,97] In summary, our preliminary studies demonstrate that in African American women with SLE, selfmanagement education delivered in weekly sessions led to improvements in lupus self-efficacy, health distress, and depression, and that more culturally targeted information and increased social support could yield more significant improvements in quality of life. More importantly, results of BLESS and IQAN studies, feedback from patients, extensive review of the literature and preliminary data from the PALS pilot study suggest that a peer mentoring intervention is credible, acceptable and likely to be effective at improving self-management, decreasing disease activity and improving quality of life in African American women with SLE. Additionally, using the same outcome measures across investigations will allow comparison of the impact of the current culturally tailored approach to the untailored "Better Choices, Better Health" intervention used in the BLESS study with this patient population.

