Disease activity will be assessed using both physician assessment and patient-reported outcome measure. The Systemic Lupus Activity Questionnaire (SLAQ)[131] asks a single Patient Global Assessment (PGA) question about presence and severity of lupus activity over the past month, questions on 24 specific symptoms of disease activity and a single Numerical Rating Scale (NRS) asking the patient to rate disease activity on a scale of 0-10 over the past three months. Use of immunomodulatory drugs and prednisone (total dose and tapers) will also be assessed. For physician assessment of disease activity, the Systemic Lupus Erythematosus Disease Activity Index (SLEDAI) has been individually validated and found reliable in clinical trials. SLEDAI scores are routinely collected as part of regular visits and clinical, demographic, genetic, disease activity/damage, genetic, and laboratory data are stored in the longitudinal web-based SLE database at MUSC as part of NIH-funded P60 and P30 grants (see [name] biosketch). All clinicians recording SLEDAI scores are trained in this assessment with annual refresher courses as part of their participation in industry-sponsored clinical trials. SLEDAI scores for each participant will be extracted from the database when available for dates within the same month as baseline, mid-intervention, and post-intervention data collection points. When scores are not available in the database, the participant will be scheduled for a clinic visit that will include vitals, blood collection, and labs to ascertain SLEDAI score. Clinic visits will take place within the South Carolina Clinical & Translational Research Institute (SCTR) Research Center (Research Nexus) at MUSC. The SC will coordinate questionnaire administration, clinic visits for SLEDAI ascertainment, and data entry. Physical examination and laboratory evaluation will be achieved by in-person clinic visit when recent SLEDAI scores are not available in the database record of a given participant. Social support control participants and mentors will complete assessments on the same schedule as mentored participants. The SLEDAI is a multicomponent, 24 question survey of clinical and laboratory signs and symptosm used as a representation of a physician's assessment of a patient's disease activity over the last 30 days (see Appendix). Items are weighted based on their severity ranging from a multiplier of 8 to no multiplier (i.e. 1). The maximum 'score' for the test is 105.[132] Validated clinically meaningful changes in SLEDAI scores are -6 for improvements and +8 for worsening disease activity.[133]

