Power and Sample Size Justification: The sample size calculation and power analyses are based on the primary outcome of change in HRQOL between baseline and 12 months post intervention. The minimum sample size was based on detecting a clinically meaningful difference of 0.35 standard deviation units (medium effect) based on prior studies.[87,93,139-143] Essentially, this is equivalent to testing the interaction between time and group. Assuming 3 measurement time points, level of significance p=0.05, two-tailed comparison, correlation between pairs of measurements within participants (interclass correlation) no larger than p=0.6, compound symmetry covariance structure, we estimate that 123 participants per group (total n=246) are needed to detect, with 80% power, a standardized effect size of at least 0.35sd. This sample size includes a 20% inflation for attrition at 12 months. This effect size is robust enough to provide sufficient power for the outcomes listed under aims 1 and 2 and is consistent with data from our pilot study of 20 mentees and 7 mentors (see preliminary data). The pre-post differences in the outcomes (such as overall social support, positive social interaction, tangible support, vitality, emotional support, social functioning, general health, coping, etc), ranged from 0.35 to 0.88 standard deviation units. Although these calculations account for within patient clustering through the intera-class correlation mentioned above, clustering within mentors and mentees are assumed to have minimal intra-class correlation based on pilot data, especially since the cluster sizes would be at most 3 at a given wave. However, a multi-level model will be used in the analysis to verify this. Since the effect size planned is conservative, if the clustering leads to higher intra-class correlation, we would still be able to detect meaningful differences. We will also consider including mentor as a fixed effect in the model.

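### The only group-level numerical stopping rule has no control-arm term, and would very rarely fire at a 0.35 SD mean worsening unless baseline scores are very widely spread

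*Combined protocol and SAP*

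**What the plan says.** The rule appears under Mid-point Analyses for the protection of participants, within Overview of Statistical Analysis Plan. It is repeated in the human-subjects section, after the steps for negative mentor-mentee interactions, and again in the safety-monitoring text. Its stated purpose is to protect participants from harmful effects of mentoring.

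- **Who is tested:** "If mentored participants have worsened beyond a threshold, we will stop the trial for ethical concerns".
- **On what:** any one of three variables, "namely depression, anxiety, and/or disease activity". Whether disease activity means SLAQ or SLEDAI is not said.
- **Criterion:** the trial stops "if the lower confidence limits based on 95% confidence interval at the midpoint" for any one of these "is larger than 50% compared with their baseline measure, the trial will be terminated". The sentence opens as an example, but no other threshold is given.
- **When:** "a mid-point (interim) analysis will be undertaken to assess safety using 3-month post-intervention data". The assessment schedule has visits at baseline and at 3, 6 and 12 months from baseline, so the label matches no scheduled visit. The number of women included is not stated.

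The document gives two benchmarks for a meaningful change. Power and Sample Size Justification uses 0.35 SD between arms for HRQOL and says this serves the outcomes of Aims 1 and 2. Methods for AIM 2 says: "Validated clinically meaningful changes in SLEDAI scores are -6 for improvements and +8 for worsening disease activity". Data Collection Process/Schedule has the support group complete its assessments on the same schedule as the mentored women.

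**The concern.** Whether mentoring does harm is a causal question, and the trial has a randomised control arm with which to answer it. The rule leaves that arm out. A worsening common to both arms counts towards stopping although mentoring did not cause it. A deficit relative to controls counts for nothing if mentored women have not themselves worsened. The second case is realistic: in the uncontrolled pilot, mean depression fell by 2.62 points and anxiety by 3.52. If, for illustration, support-group women improved by those amounts and mentored women did not change, the rule would see nothing.

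The size of the criterion is the second issue. It is the lower limit, not the estimate, that must pass 50%, and one percentage of baseline is applied to scales with different means and spreads. The plan does not report how often the rule would trigger, with or without harm. The principal investigator acts as safety monitor and no independent committee is described, so the wording of the rule carries much of the weight.

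**Working it through.** **Inputs from the documents.** Effect 0.35 SD, correlation 0.6 with compound symmetry, two-sided 0.05 and 80% power (Power and Sample Size Justification); 50 mentored women per wave and 150 in all (Study Overview).

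**Inputs assumed.** The coefficient of variation at baseline (CV = SD/mean) is not given and is varied. The interim number is taken as 50 to 150 mentored women.

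**Plan's own figure.** The variance of change in SD units is 2(1 − 0.6) = 0.8. Per arm, n = 2 × 0.8 × (1.96 + 0.842)² / 0.35² = 102.5, and 102.5 × 1.2 = 123.0. This matches the stated 123 per group, so the variance used below is the plan's own.

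**Chance that the rule fires.** A 50% rise equals 0.5/CV in SD units. For a true mean worsening d, with the baseline mean treated as fixed:

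P = Φ[(d − 0.5/CV) / √(0.8/n) − 1.96]

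At d = 0.35, for one variable:

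| CV | 50% rise, in SD | P, n = 50 | P, n = 150 |
|---|---|---|---|
| 0.8 | 0.63 | 0.002% | <0.001% |
| 1.0 | 0.50 | 0.08% | 0.003% |
| 1.2 | 0.42 | 0.64% | 0.20% |
| 1.43 | 0.35 | 2.5% | 2.5% |
| 2.0 | 0.25 | 12% | 28% |

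Worked entry (CV 1.0, n = 50): (0.35 − 0.50)/0.1265 − 1.96 = −3.15, so P = 0.08%. Since any one of three variables can trigger the rule, the overall chance is at most three times the entry if all three worsen by 0.35 SD.

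**Harm needed for an 80% chance of firing.** d = 0.5/CV + 2.80 × √(0.8/n). At n = 150 this is 1.04 SD (CV 0.6), 0.83 SD (CV 0.8) and 0.70 SD (CV 1.0), two to three times 0.35 SD.

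**Sensitivity.** With correlation 0.7, the figure used in the Scientific Rigor paragraph, n = 50 gives 0.04% at CV 1.0 and 0.51% at CV 1.2. If an ordinary interval for the mean change is instead compared with 50% of the *observed* baseline mean, that mean's sampling error adds noise: the variance of follow-up minus 1.5 × baseline is 1 + 2.25 − 3 × 0.6 = 1.45. Then P = Φ[(0.35 − 0.5/CV − 1.96√(0.8/n)) / √(1.45/n)], which at n = 50 is about 1.0% at CV 1.0 and 3.2% at CV 1.2. The chance stays low, but its exact value depends on how the interval is built, which the plan does not say.

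**SLEDAI +8, read as a mean shift.** It exceeds 50% whenever the baseline mean is below 16. With n = 50 or 150, CV 0.6 or 1.0 and a fixed baseline mean, the rule fires at least 97% of the time for baseline means up to 8, 26% to 97% at 12, and 2.5% at 16.

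**Between-arm comparison, for illustration.** Power at 0.35 SD is Φ[0.35/√(1.6/n) − 1.96]: 50% with 50 per arm and 86% with 120 per arm.

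**The case against.** A reader might infer that the rule cannot detect any harm the trial itself calls meaningful. The documents do not support that. The 0.35 SD is a between-arm HRQOL figure extended to Aims 1 and 2, which reaches disease activity. Depression and anxiety are listed as covariates, so applying it to them is an assumption. The one meaningful worsening defined for a possible stopping variable is SLEDAI +8, and a mean shift of that size would usually be caught at low baseline means. Nor is +8 in direct contradiction with 50%: it reads most naturally as a change in one patient, whereas the rule concerns a group.

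A reader might also take this rule to be the only safeguard. It is not. The protocol provides clinician assessment of women who screen positive for depression, screening before pairing, bi-weekly contact by the investigator, reassignment of mentors, and adverse-event reporting. It is the only group-level numerical trigger. Between-arm comparisons are also planned for each wave and in the Aim 2 models, but nothing links them to stopping.

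Two further inferences are weak. Regression to the mean is a poor reason to expect a shared rise, since the study overview describes the women as having active SLE. The pilot's percentages, which appear to be taken against the scale range, do not redefine a rule that names baseline as its base.

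The strongest objection is that stopping for absolute worsening has an ethical purpose of its own: a purely between-arm rule would stay silent if both arms deteriorated. That stands, and is why the comparison should be added to the present check and not replace it.

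**Conclusion.** The concern holds in this form. The missing control-arm term is plain from the text and needs no assumption: as written, the rule cannot attribute a change to mentoring and can miss a deficit relative to controls.

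The low sensitivity is conditional. At a 0.35 SD mean worsening, with correlation 0.6, 50 to 150 women and a fixed baseline mean, the rule fires on a given variable less than 0.1% of the time for CV up to 1.0 and at most about 0.6% at CV 1.2. Allowing for an estimated baseline mean raises these to about 1% and 3% at n = 50. A baseline SD well above the mean would raise them further. If the 50% is only an example, the rule has no specified threshold, which is no better. The change should be made, but this is a weakness of specification and comparator, not proof that participants are unprotected.

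**What to change.** In all three places where the rule is stated:

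1. Keep the within-arm check and add the mentored-minus-support-group difference in change from baseline, by randomised group, with its 95% confidence interval, for depression, anxiety and each disease activity measure, named.
2. State which scheduled assessment is used, how many women are included, and how the interval and the percentage are calculated.
3. Report the chance of triggering under no harm and under a 0.35 SD harm.
4. Have the sponsor say whether 50% is the threshold or an example, and reconcile one percentage for all scales with the benchmarks in Power and Sample Size Justification and Methods for AIM 2. No threshold is proposed here.

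The cost is wording and some calculation; the control data are already collected. The downsides are a wider interval for the two-arm difference (hence only about 50% power with 50 per arm) and a mid-point summary by arm, access to which should be restricted.
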